In the past decade, multiple myeloma patients have reached deeper response rates with use of effective anti-myeloma therapeutics, immunomodulatory agents and proteasome inhibitors, approximating up to 75% patients achieving near-complete response (>90% decrease in monoclonal protein) or complete response (100% decrease in monoclonal protein). In general, improved therapeutics and deeper response rates have resulted in improved overall survival of multiple myeloma patients across most age groups. As a result, there has been an increasing demand for the development of sensitive assays to detect minimal residual disease (MRD) in treated MM patients. In MM patients receiving autologous stem cell transplant, MRD-negative status using multi-parametric flow cytometry (MFC) is associated with improved progression free survival and overall survival. Similar studies using next generation sequencing methods for MRD have also been shown to be associated with improved outcomes in MM MRD-negative patients. In our prior study, among the 25 patients with CR/sCR that were assessed by MFC for immunophenotypic abnormal plasma cells; 25 out of 25 were negative for (MRD with an overall MRD negative rate of 25/43 (58)% (*2 patients did not have evaluable samples) using MFC. Using next generation sequencing molecular tests, the CR/sCR MRD negative rate was 13/33 (39%) (*12 patients did not have evaluable samples) (Sequentia platform). In patients with NDMM treated with CRd, 12-month progression-free survival for MRD-negative vs MRD-positive status by flow cytometry and next-generation sequencing was 100% vs 79% (95% CI, 47%-94%; $P < .001$) and 100% vs 95% (95% CI, 75%-99%; $P = .02$), respectively.

Minimal Residual Disease Platforms

A recent survey including 30 major institutions in the US found major heterogeneity in MRD testing of multiple myeloma by flow cytometry²². In brief, there was considerable variation in the number of bone marrow cells analyzed (events) and number of abnormal plasma cells needed to define the presence of MRD, which affects maximum possible sensitivity. The maximum detection sensitivity ranged from 0.0005% to 0.02%, a 100-fold difference in sensitivity. Also, the variation in antibodies studied and definition of an abnormal plasma cell by flow cytometry affected the ability to differentiate normal from neoplastic plasma cells.

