In 2015, the Department of Laboratory Medicine developed, validated and implemented in the 10-color platform in collaboration with the Myeloma Service and the International Myeloma Foundation. The MSK single tube 10-color flow cytometry platform demonstrates similar results to Euroflow and is already in use under clinical practice. Because there is currently no data available to compare the sensitivity of the MSK model and molecular MRD assays, as a secondary endpoint, we will compare our 10-color flow cytometry platform against next generation sequencing and mass spectrometry. These studies will help us to better understand and further develop details of various MRD methods.

Daratumumab in Combination with Carfilzomib, Dexamethasone and Lenalidomide

The results of the interim analysis show 11 participants have reached MRD negativity with an average of 5.36 cycles in Cohort 1 while 10 participants have reached MRD negativity with an average of 4.5 cycles in Cohort 2. There are 2 participants and 18 participants pending a best MRD response within 8 cycles of combination therapy for Cohort 1 and 2, respectively. As of May 2019, Cohort 2 has shown a 100% MRD negativity rate as a best response within 8 cycles of combination therapy. Cohort 2 is based on weekly dosing schedule that reduces the number of visits by 50% from Cohort 1 with Carfilzomib 56 mg/m² per dose.

Randomization Cohort Treatment Arms

Randomization allows objectivity for assigning treatment arms. Attal et al. published results that showed participants treated with RVD induction therapy achieved MRD negativity at 65%. However, overall survival at 4 years between the transplantation group and the RVD only alone group was similar (81% and 82%, respectively)⁴⁷. In a later study, Perrot et al. showed 25% MRD negativity was achieved at least once during maintenance with in 127 patients who were treated with RVD induction therapy alone⁴⁸.

Evidence supports KRd induction is favorable induction therapy for NDMM and SMM as one study has shown 28 patients with NDMM and the 12 with SMM achieved a-near CR with 28 of 28 found to be MRD negative from the JAMA Oncology paper on the NCI KRd phase 2 study (Korde et al, 2015)⁴⁹.

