 - Appearance of any other sign of progression (i.e., new plasmacytoma, lytic bone lesion, hypercalcemia)

MRD Response Criteria based on 2018 definition for Multiple Myeloma^{22, 27, 28}

Evaluation of Response Criteria

- a) VGPR/CR and MRD 10^{-5} negative in the bone marrow: absence of phenotypically aberrant clonal plasma cells by multicolor flow cytometry and/or next generation sequencing on bone marrow aspirates using a validated method with a sensitivity of at least 1 in 10^{-5} nucleated cells.
- b) VGPR/CR but MRD positive in the bone marrow: VGPR/CR as defined above but with presence of phenotypically aberrant clonal plasma cells by multicolor flow cytometry and/or next generation sequencing on bone marrow aspirates using a validated method with a sensitivity of at least 1 in 10^{-5} nucleated cells.
- c) Imaging plus MRD Negative: MRD negativity as defined by multicolor flow cytometry and/or next generation sequencing (as defined above) plus disappearance of areas of increased tracer uptake found at baseline or preceding PET/CT or decrease to less mediastinal blood pool SUV or decreased to less than that of surrounding normal tissue.

We note that while the IMWG includes both MFC and next generation sequencing in their response definition, only MFC will be used for our primary endpoint definition. Next generation sequencing will be investigated as a secondary endpoint.

Progression-Free Survival

PFS is defined as time of start of treatment to time of progression or death, whichever occurs first.

Overall Survival

Overall survival is defined as the time of start of treatment to death from any cause.

Toxicity Criteria

The following adverse event management guidelines are intended to ensure the safety of each patient while on the study. The descriptions and grading scales found in the revised NCI Common Terminology Criteria for Adverse Events (CTCAE) version 4.0 will be utilized for AE reporting. All appropriate treatment areas should have access to a copy of the CTCAE version 4.0. A copy of the CTCAE version 4.0 can be downloaded from the CTEP web site (http://ctep.cancer.gov/protocolDevelopment/electronic_applications/ctc.htm#ctc_40).

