14.0 BIOSTATISTICS

Primary Objective:

This is a phase II study to assess the efficacy of up to 8 cycles of combinational therapy with daratumumab, carfilzomib, lenalidomide, and dexamethasone in newly diagnosed multiple myeloma (MM) patients. The primary objective of the study is to assess the rate of MRD negativity at the end of planned treatment up to 8 cycles for the combination therapy using multiparametric flow cytometry. Patients with < PR after completing 4 cycles will be included in the analysis of the primary objective and will be considered MRD positive. Patients who receive any study drug and have at least one post-baseline disease assessment will be considered evaluable for the primary endpoint. The rate of MRD negativity will be assessed for each cohort, separately.

This study is designed to distinguish between an unpromising MRD rate of 40% and a promising rate of 60%¹. The unpromising rate of 40% is based on the 1st generation sequencing-based MRD rate in the referenced Korde et al study. The flow cytometry-based MRD assessment that will be used as part of this study has been shown to have similar performance as the sequencing-based MRD assessment used in that study.

The study includes two cohorts, which of each will receive up to 8 cycles of combination therapy. The two cohorts are defined based on the schedule and dosing of carfilzomib. These cohorts are described in Section 4.0. The following Simon two-stage design will be evaluated separately for the two cohorts.

Using a Simon's minimax two-stage design, the first stage of the study will enroll 28 patients. If at least 12 have a best response of MRD negativity within 8 cycles of therapy, the study will continue to enroll remaining patients up to a total of 41 patients. If, after 28 patients have accrued, it is uncertain whether the response threshold will be met, accrual will be held until the determination can be made. If 21 of the 41 patients have a best response of MRD negativity within 8 cycles of therapy the study will be considered to be successful. The study is designed to have a type I error and a type II error of 0.10. The maximum sample size is 41 patients.

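### The 40% null is a sequencing-based rate applied to a flow-only endpoint, so the stated type I error does not protect against a cohort that merely matches KRd by flow

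*Combined protocol and SAP*

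**What the plan says.** Section 14.0 sets up each cohort to distinguish "an unpromising MRD rate of 40% and a promising rate of 60" per cent. On the source of the lower figure it says: "The unpromising rate of 40% is based on the 1st generation sequencing-based MRD rate". It adds that the flow assay to be used here "has been shown to have similar performance as the sequencing-based MRD assessment used in that study".

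The design is a Simon minimax two-stage: "the first stage of the study will enroll 28 patients", the cohort continues with at least 12 MRD-negative patients, and it is called successful with 21 of 41. On error rates: "The study is designed to have a type I error and a type II error of 0.10".

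Section 12.0 fixes the assay for the endpoint: "only MFC will be used for our primary endpoint definition". It also lets VGPR patients count as MRD negative, and it counts undeterminable MRD as positive.

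Section 3.0 (Minimal Residual Disease Testing in Myeloma) gives both rates from the earlier KRd study. By sequencing it was 13/33 (39%). By flow it reports an "overall MRD negative rate of 25/43 (58" per cent), with two patients not evaluable, and all 25 CR/sCR patients assessed were flow negative. The next subsection, on MRD platforms, says that "there is currently no data available to compare the sensitivity of the MSK model and molecular MRD assays" and makes that comparison a secondary endpoint.

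**The concern.** The trial has no randomized control (Section 15.2), so the historical rate is its only comparator. The sponsor chose the KRd study as the benchmark but took the rate from an assay that is not the endpoint. The flow rate from the same study is close to the 60% that the plan calls promising, and the final bar of 21/41 = 51% lies below it.

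The one sentence that would justify crossing assays conflicts with Section 3.0. The similarity that Sections 3.0 and 12.0 do assert for the site's flow assay is to Euroflow, not to sequencing.

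What is at stake is the meaning of a successful cohort. A reader will take it as a gain from adding daratumumab to KRd. Meeting 21/41 does not support that reading if KRd alone already yields a flow rate in the fifties.

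**Working it through.** **Inputs.** From Section 14.0: n1 = 28, continue at ≥12; N = 41, success at ≥21; p0 = 0.40; p1 = 0.60; both errors 0.10. From Section 3.0: KRd by flow 25/43, two not evaluable; by sequencing 13/33 = 39.4%. From Section 12.0: undeterminable MRD counts as positive, so the matching historical figure is 25/(43 + 2) = 25/45 = 55.6%.

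**Formula.** For true rate p, the exact probability of success is

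P(success) = Σ from x = 12 to 28 of C(28, x) p^x (1 − p)^(28 − x) × P[Bin(13, p) ≥ 21 − x].

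**Reproducing the plan.** At p = 0.40 this gives 0.0951; at p = 0.60 it gives 0.9009. A search for the smallest N meeting both error limits returns this same design. The arithmetic in Section 14.0 is correct.

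**The same rule at other no-benefit rates (per cohort).**

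| True rate with no gain over KRd | P(declared successful) | P(stop at stage 1) |
|---|---|---|
| 40% (plan's null) | 0.095 | 0.55 |
| 42.1% (lower 95% limit of 25/43) | 0.15 | 0.46 |
| 45% | 0.26 | 0.34 |
| 50% | 0.50 | 0.17 |
| 55% | 0.74 | 0.07 |
| 55.6% (25/45) | 0.76 | 0.06 |
| 58.1% (25/43) | 0.85 | 0.03 |
| 60% (plan's alternative) | 0.90 | 0.02 |

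**Uncertainty in the benchmark.** The exact 95% interval for 25/43 is 42.1% to 73.0%. Across it, P(success) runs from 0.15 to 0.999.

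**What a flow-based comparison would need in 41 patients.** With the stage 1 rule unchanged and a final bar of ≥29/41, P(success) is 0.066 at 58%; ≥28/41 gives 0.119, above 0.10. With ≥29/41, power is 0.90 at 78%, 0.79 at 75% and 0.54 at 70%. The 78% is an assumption (58% plus the plan's 20-point gap) with no source in the documents.

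Exact two-sided 95% lower limits are 35.1% at 21/41, 54.5% at 29/41, 57.1% at 30/41 and 59.7% at 31/41. A 95% lower limit above 56% therefore needs 30/41, and above 58% needs 31/41.

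**The case against.** The strongest reply is that 58% is not KRd's rate under this trial's endpoint. Four parts of it deserve weight.

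- **Precision.** The figure comes from 43 patients. This stands, and it is why the result must be given as a range.
- **Assay.** The 25/43 came from an earlier study at another institution. This trial uses the site's 10-color assay, developed in 2015 and stated to detect 1 cell in 100,000 or better. Section 3.0 itself stresses how widely flow assays differ. A more sensitive assay could bring KRd's rate below 58%. This stands. It also means that the 58% versus 39% contrast does not by itself refute the similar-performance sentence, which concerns the newer assay. What undercuts that sentence is the statement in Section 3.0 that no comparative data exist.
- **Time window.** In the earlier study, time to sCR ranged from 2 to 18 cycles, with lenalidomide maintenance after cycle 8. This trial counts only 8 cycles, so 58% may include later responses. This stands, although crediting VGPR patients pushes the no-benefit rate the other way. The documents allow neither effect to be sized.
- **Wording.** The type I error does hold at the null that the plan states. This also stands: the fault is in the choice and justification of the benchmark.

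A reader might infer that a cohort with no daratumumab benefit will be declared successful 85% of the time. The documents do not support that as an unconditional statement, because it requires 58% to be the true KRd rate under this endpoint. A reader might also infer that the success rule must be replaced by a 58% versus 78% design. That does not follow either: 78% is unsourced, power at 70% would be only 0.54, and Section 3.0 already reports interim MRD results.

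None of these points supports 40%. They show that the flow rate is uncertain, and the plan's only argument for 40% is the sentence that Section 3.0 contradicts.

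**Conclusion.** Wrong as written. The null comes from a different assay than the endpoint, and the bridge between the two is contradicted within the same document. The stated type I error (0.095 exactly) applies only if KRd alone would give 40% under this trial's endpoint.

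If KRd's flow rate is 56% to 58%, a cohort with no gain meets the rule with probability about 0.76 to 0.85. Even at the lower 95% limit of 42%, the probability is 0.15, above the stated 0.10. The assay mismatch and the internal contradiction are certain. The size of the inflation is conditional on a benchmark drawn from 43 patients, an earlier flow assay and possibly a longer response window.

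**What to change.** 1. Reconcile Section 14.0 with Section 3.0 by withdrawing the claim of similar performance, since the protocol reports no data for it.
2. State in Section 14.0 that meeting 21/41 tests only against a 40% sequencing-based rate, at a one-sided 0.10 level, and does not show a gain over KRd by flow.
3. Tabulate the operating characteristics of the existing rule for true rates from 40% to 60%.
4. Report each cohort's MRD-negative rate with an exact confidence interval beside the flow-based KRd benchmark (56% to 58%), and allow a claim of improvement over KRd only if the lower limit exceeds it. Fix the benchmark value and confidence level in advance. Section 14.0 already plans exact 95% intervals for the response rates.
5. Optionally, show ≥29/41 as an illustration beside the 21/41 rule, with its properties (0.066 at 58%; power 0.90 at an assumed 78%, 0.54 at 70%). It should not be a required replacement, because interim results are known. It is also a less strict standard than a 95% lower limit above 58%, which needs 31/41.

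**Cost.** An amendment to the wording of Section 14.0 and a short table. No extra patients are needed, and the 28/41 structure and its rule stay in place. The price is a less favourable success claim: a cohort can meet the protocol rule and still not support a statement that the combination improves on KRd.

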1.0 PROTOCOL SUMMARY AND/OR SCHEMA

This is a phase II study to assess the safety and efficacy of 8 cycles of combinational therapy with DARZALEX™ (daratumumab), carfilzomib, lenalidomide, and dexamethasone in newly diagnosed multiple myeloma (MM) patients.

Primary Objective:

The primary objective of the study is to assess the rate of MRD negativity after completion of the combination therapy using multiparametric flow cytometry

Secondary Objectives:

1. To determine safety and tolerability.
2. To evaluate the rates of overall response (partial response (PR) or better), very good partial response (VGPR) or better, and complete response (CR) or stringent CR (sCR). See section 12.0 for response definitions.
3. To estimate overall survival (OS) and progression-free survival(PFS).
4. To compare MRD techniques of multi-parametric flow cytometry with next-generation sequencing and mass spectrometry.
5. To create a bone marrow, urine, stool, and peripheral blood sample bank. These samples may be used to later-evaluate biological activity of daratumumab, carfilzomib, lenalidomide, and dexamethasone. Potential analyses include sequencing and gene expression profiling on pre and post therapy bone marrow samples, identification of potential biomarkers (blood, urine, stool, bone marrow aspirates) associated with clinical outcomes.

Exploratory Objectives:

1. The gene panel myTYPE will explore whether any mutations appear to be associated with response to therapy or toxicity.
2. myTYPE will be evaluated using samples at the time of progression of disease or during an ongoing response and will be compared to the pre-treatment baseline samples to explore whether pathways leading to emergence of resistance to the drug regimen can be identified.
3. To evaluate the effects on stem cell mobilization quality in patients receiving daratumumab, carfilzomib, lenalidomide, and dexamethasone. Examples of data being collected but not limited to will include the following: number of patients undergoing stem cell mobilization, demographics, cycles received prior to stem cell mobilization, CD34 blood counts prior to collection, total stem cell yield, mobilization failure rates, and subsequent attempts of mobilization.

Patient Population

Newly diagnosed patients with histologically confirmed multiple myeloma.

Study Design

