- h. Bone marrow aspirate and biopsy can be performed +/- 21 days of intended cycle day or achievement of CR/sCR. Bone marrow aspirate and biopsy will be sent to evaluate for histopathology, flow cytometry (bone marrow immunophenotyping of plasma cells), heavy/light chain immunoglobulin rearrangement. Aspirate lysate will also be sent for cell sorting into CD 138- and + fractions and whole bone marrow lysate for HOTB storage so molecular profiling with GEP and DNA-based sequencing at baseline can be performed as correlative work. For patients, reaching CR/sCR MRD negative timepoint earlier where MRD negative status is confirmed at earlier bone marrow evaluation, bone marrow aspiration and biopsy at end of study will be as per standard of care. Otherwise, all other bone marrow biopsies are strongly encourage for all cohorts.
- i. After study therapy ends at the completion of 8 cycles or after 4 cycles in patients who have <PR, follow-up will be 1 month after study end date. Patients may be followed at more frequent time intervals, and thereafter if clinically indicated. Patients who have progressive disease while on therapy will be followed with restaging scans and laboratory tests as clinically indicated. At disease progression, marrow and FDG-PET/CT are optional but recommended.
- j. For patients with initial baseline 24-hr UPEP samples demonstrating ≥ 100 mg/24 hrs, patients will continue to have 24-hr UPEP samples day 1 of each cycle. Once 24-hr UPEP is < 100 mg/24 hrs, patient can have random UPEP with IFE until achieving negativity. If initial baseline 24-hr UPEP sample is IFE positive and/or < 100 mg/24, patients can have random UPEP samples with IFE until achieving negativity. Once random UPEP and IFE is negative, no further urine samples are needed (unless patient's disease is primarily measurable by 24 hr urines)
- k. FDG-PET scan will be performed on patients at baseline, end of therapy or upon suspicion of progressive disease as clinically indicated..
- l. Variations of +/- 7 days of scheduled visits are permitted (Treatment window for day 1 of start of each cycle is +/- 7 days. Treatment window for intra-cycle carfilzomib and/or daratumumab doses is +/- 2 days). Patients who have completed 1 cycle of standard of care therapy who meet eligibility criteria and have had a PET scan read at MSK within 60 days of cycle 1 day 1, will not need an additional PET scan read at MSK within 60 days of cycle 1 day 1, unless clinically indicated.

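### The primary objective is an end-of-therapy MRD-negative rate, but both Simon decisions count best MRD response at any time within 8 cycles, and the plan does not reconcile the two

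*Combined protocol and SAP*

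**What the plan says.** **Objective.** Sections 1.0 and 2.0 say that the trial will "assess the rate of MRD negativity after completion of the combination therapy using multiparametric flow cytometry". The first paragraph of Section 14.0 says it will "assess the rate of MRD negativity at the end of planned treatment up to 8 cycles". Both describe status at a fixed point, when treatment is over.

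**Decision rule.** Later in Section 14.0, both Simon cut-offs use best response. Stage 1 continues if at least 12 of 28 patients have been MRD-negative as best response within 8 cycles. The cohort is successful if "21 of the 41 patients have a best response of MRD negativity within 8 cycles of therapy". The interim results in Section 3.0 are also reported as best response.

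**When MRD is measured.** Section 9.4.4 and the Section 10.0 tables schedule marrow flow cytometry when CR/sCR is reached and at end of therapy. Footnote h of Section 10.0 then makes an exception. For patients with an earlier confirmed CR/sCR MRD-negative marrow, "bone marrow aspiration and biopsy at end of study will be as per standard of care".

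**Counting rules.** Patients below PR after 4 cycles count as MRD-positive (Section 14.0), as do patients in VGPR or better whose MRD status cannot be determined (Section 12.0). No rule covers a patient who is MRD-negative early and then turns positive, relapses from CR, progresses or dies before the end-of-therapy evaluation.

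**The concern.** The stated objective and the quantity that decides the trial are different endpoints, and both appear in Section 14.0. One asks how many patients are MRD-negative when treatment ends. The other asks how many were ever MRD-negative during treatment. Followed as written, the plan would produce an ever-negative rate and report it under an end-of-therapy label.

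The two can differ only through patients who are negative early and lose that status. That is also the group for whom footnote h does not require an end-of-therapy marrow. The group may be large: Section 3.0 reports that those who reached negativity did so after an average of 5.36 cycles in Cohort 1 (11 patients) and 4.5 cycles in Cohort 2 (10 patients), well before cycle 8. On the literal rule, a patient negative at cycle 4 who has progressed by cycle 8 is a success.

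At stake are the meaning of the reported rate and, depending on what the 40% null refers to, the type I error of each cohort's decision.

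**Working it through.** **Inputs from Section 14.0, per cohort.** Unpromising rate 40%, promising rate 60%; type I and type II error 0.10; n1 = 28, continue if at least 12; N = 41, success if at least 21.

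**Step 1. Reproduce the design.** With p the probability that a patient is counted as MRD-negative,

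P(success | p) = Σ from x = 12 to 28 of b(x; 28, p) × P[Bin(13, p) ≥ 21 − x].

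- p = 0.40: 0.0951, the exact type I error.
- p = 0.60: 0.9009, the exact power.
- Probability of stopping after stage 1 at p = 0.40: 0.551.

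An exhaustive minimax search with type I error at most 0.10 and power at least 0.90 returns the same design (28, 12, 41, 21). The arithmetic is right for whichever endpoint is counted.

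**Step 2. Direction of the difference.** For each patient, best response is at least as favourable as end-of-therapy status. Let f be the share of ever-negative patients who are no longer negative at end of therapy. Then

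end-of-therapy rate = ever-negative rate × (1 − f).

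The documents give no value for f. The values below are assumptions, and f = 0 is possible.

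**Step 3. If the 40% null is an end-of-therapy rate.** The rule then sees an ever-negative rate of 0.40/(1 − f).

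| Assumed f | Rate seen by the rule | Expected count in 41 | P(success) |
|---|---|---|---|
| 0 | 0.400 | 16.4 | 0.095 |
| 2% | 0.40/0.98 = 0.408 | 16.7 | 0.115 |
| 5% | 0.40/0.95 = 0.421 | 17.3 | 0.151 |
| 10% | 0.40/0.90 = 0.444 | 18.2 | 0.234 |

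The 10% row is a difference of under two patients in the expected count (18.2 − 16.4 = 1.8). At the boundary one patient decides: 21 ever-negatives with one reversion is 20 at end of therapy, below the cut-off.

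**Step 4. If the 40% null is a best-response rate.** The rule tests like against like. P(success) at the null is 0.095 whatever f is. Only the label on the objective is wrong.

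**Step 5. The reverse case.** If 60% was meant as a best-response rate and the rule were applied to end-of-therapy status, the rate seen would be 0.60 × (1 − f). Power is 0.901 at f = 0, 0.814 at f = 5% (rate 0.57) and 0.693 at f = 10% (rate 0.54). The basis of both rates therefore has to be stated, not only that of the null.

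**Step 6. Which basis do the documents give?** Section 14.0 takes the 40% from the earlier KRd study, and Section 3.0 gives the figure as 13/33 (39%) by sequencing among CR/sCR assessments. Neither says when MRD was tested. Section 3.0 does report time to sCR in that study over a range of 2 to 18 cycles, beyond its eight KRd cycles. That fits a best-response benchmark but does not establish one.

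**The case against.** The strongest defence is that the deciding endpoint is clear. Best response within 8 cycles is pre-specified, stated at both Simon cut-offs and used for the interim report. The design is a correct minimax design for that quantity. The objective can be read as saying when the rate is tallied rather than when each patient's status is taken. This stands as far as it goes: the rule is usable and its error rates are right for the ever-negative rate. It does not remove the mismatch, because the objective's wording describes status at or after the end of treatment and no text links the two.

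Two stronger readings are tempting, and the documents do not support them.

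- *That success is overstated.* A reader might infer this from the direction of the difference. But no reversion rate is given, the excess may be zero, and if the 40% is a best-response rate the type I error is not inflated at all.
- *That the end-of-therapy rate is not measured.* This is too broad. Flow cytometry at end of therapy is scheduled. Footnote h relaxes it only for confirmed CR/sCR negatives and does not name patients who are negative in VGPR. Some exempt patients will have a standard-of-care marrow anyway. The result is not guaranteed for early negatives, which is a narrower statement.

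Nor does repeat testing alone give patients an unfair second chance. For a patient who is positive at CR and retested at end of therapy, the second test is the end-of-therapy result. Only an early negative that does not last can separate the two rates.

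**Conclusion.** The inconsistency is real and should be corrected. The objective names an end-of-therapy rate, the decision counts an ever-negative rate, and the plan neither secures the end-of-therapy marrow for early negatives nor says how a lost negative is counted.

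Its effect on the decision is conditional. With a 40% null on an end-of-therapy basis, the false-success probability exceeds the nominal 0.10 at an assumed loss of 2% of ever-negative patients (0.115) and reaches 0.234 at 10%. With a best-response null it remains 0.095. The loss rates are assumptions, and the documents do not settle the basis of the null, so the conclusion is that success can be overstated relative to the stated objective, not that it is.

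The sample size and cut-offs are sound and need no change if 40% and 60% are kept.

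**What to change.** Use one endpoint in Sections 1.0, 2.0 and 14.0. The simplest course is to align the objective with the rule:

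1. Reword the primary objective in all three sections as *rate of MRD negativity by multiparametric flow cytometry as best response within 8 cycles*.
2. State in Section 14.0 that the 40% and 60% are on that basis, after confirming the time point of the 40% benchmark from its source.
3. Do not describe the result anywhere as a rate after completion of therapy.
4. Add a sensitivity analysis for each cohort. Recount after reclassifying as failures any early negatives with a later MRD-positive marrow, relapse from CR, progression or death before the end-of-therapy evaluation, using assessments already done.
5. State the limits of that recount. Reversion visible only in marrow may be missed where no further marrow is taken. Urine testing may also have stopped once negative (Section 9.4.2, footnote j of Section 10.0, and Section 12.0). For these reasons the recount belongs beside the primary analysis and should not replace it.

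Cost: text in three sections and one extra tabulation. There is no new procedure, and N and the cut-offs are unchanged. The downside is that the sensitivity count may be slightly less favourable than the headline.

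If the sponsor prefers a true end-of-therapy endpoint, the costlier alternative is to obtain a flow result at end of therapy for every patient, and to pre-specify how reversion, progression and a missing marrow are counted.
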